2. Stable non-enhancing (T2/FLAIR) lesions on same or lower dose of corticosteroids compared to baseline scan. IN the event that the corticosteroid dose was increased for new symptoms and signs without confirmation of disease progression on neuroimaging, and subsequent follow-up imaging shows that this increase in corticosteroids was required because of disease progression, the last scan considered to show stable disease will be the scan obtained when the corticosteroid use was equivalent to the baseline dose.
3. Patients must be stable clinically.#

Progressive Disease

Defined by ANY of the following:

1. Greater than 25% increase in the sum of the products of perpendicular diameters of enhancing lesions compared to the smallest tumor measurement obtained either at baseline (if no decrease) or best response, on stable or increasing doses of corticosteroids.**
2. Significant increase in T2/FLAIR non-enhancing lesion on stable or increasing doses of corticosteroids compared to baseline scan or best response following initiation of therapy,* not due to co-morbid events (e.g. radiation therapy, demyelination, ischemic injury, infection, seizures, post-operative changes, or other treatment effects).
3. Any new lesion.
4. Clear clinical deterioration not attributable to other causes apart from the tumor (e.g. seizures, medication side effects, complications of therapy, cerebrovascular events, infection, etc.) or changes in corticosteroid dose.#
5. Failure to return for evaluation due to death or deteriorating condition.
6. Unequivocal progression of non-measurable disease.

*Patients with non-measurable disease only cannot have a complete or partial response. The best response possible is stable disease.

**Stable doses of corticosteroids include patients not on corticosteroids.

#Clinical status will be assessed via ECOG Performance Score.

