9.4 Evaluation of Best Overall Response

The best overall response is the best response recorded from the start of the treatment until disease progression/recurrence and is determined as indicated in the table below:

The table below provides the summary of the RANO response criteria.

Criterion	Complete Response	Partial Response	Stable Disease	Progressive Disease
T1/Gd enhanced lesions	None	≥50% decrease	≤50% decrease to <25% increase	≥25% increase*
T2/FLAIR	Stable or decreasing	Stable or decreasing	Stable or decreasing	Increasing*
New Lesion	None	None	None	Present*
Corticosteroids	None	Stable or decreasing	Stable or decreasing	NA**
Clinical Status#	Stable or improving	Stable or improving	Stable or improving	Worsening*
Requirement for Response	ALL	ALL	ALL	Any*

*Progressive Disease occurs when any of the criteria marked by * are present.

**Increase in corticosteroid dose in isolation of other criteria will not be taken into account in the assessment of progressive disease in the absence of persistent clinical status deterioration.

#Clinical status will be assessed via ECOG Performance Score

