10.2. Appendix 1.2 Censoring for Time to Event Data

Table 4 summarizes the censoring rules for the PFS analysis and displays censoring hierarchy for this study. Table 5 shows the general reasons for PFS censoring and where the censoring hierarchy in **Table 4** came from.

Table 4 Event or Censor Time for PFS and Censoring Hierarchy

Censoring Hierarchy	Situation	Date of Event or Censor	Event / Censor
1	No baseline radiological tumor assessment available	Date of First Dose	Censored
2	New anticancer treatment started and no tumor progression	Date of previous adequate radiological assessment immediately prior to start of new therapy or Date of first dose, whichever comes later	Censored
3	Tumor progression (per RANO) documented after 2 scan intervals following previous adequate radiological tumor assessment	Date of previous adequate radiological assessment or Date of first dose, whichever comes later	Censored
4, 5	No tumor progression (per RANO) and subject lost to follow-up or withdrawal of consent	Date of last adequate radiological Assessment or Date of first dose, whichever comes later	Censored
6	No post baseline radiological tumor assessment available and no death reported within 2 scan intervals following the date of the first dose of study drug (BBI608)	Date of First Dose	Censored
7	No post baseline radiological tumor assessment available but death reported within 2 scan intervals following the date of the first dose of study drug (BBI608)	Date of Death	Event

	No tumor progression (per RANO) and no death reported within 2 scan intervals following last adequate radiological tumor assessment	Date of last adequate radiological tumor assessment or Date of first dose, whichever comes later	Censored
	No tumor progression (per RANO) but death reported within 2 scan intervals following last adequate radiological tumor assessment	Date of death	Event
	Tumor progression (per RANO) documented within 2 scan intervals following previous adequate radiological tumor assessment	Earliest of the target, non-target and new tumor assessment dates	Event

Notes: (1) Symptomatic deteriorations (i.e. symptomatic progressions, which are not radiographically confirmed) will not be considered as progressions.

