(2) If target, non-target and new lesion assessments have different dates within a visit, then the earliest of those dates will be considered as the date of the tumor assessment if the assessment for that visit is progressive disease (PD); otherwise the latest date will be used.

(3) Adequate radiographical tumor assessment refers to an assessment with overall response of CR, PR, SD or PD.

(4) Comparing date of last tumor assessment to date of first dose is necessary if the last tumor assessment is baseline assessment

Table 5 PFS Censoring Reasons and Hierarchy

Hierarchy	Condition	Censoring Reason
1	No adequate baseline assessment	No adequate baseline assessment
2	Start of new anti-cancer therapy before event.	Start of new anti-cancer therapy
3	Event more than 2 weeks from last adequate post-baseline tumor assessment/start date	Event after missing assessments ^a
4	No event and [withdrawal of consent date \geq start date OR End of study (EOS) = Subject refused further FU]	Withdrawal of consent
5	No event and lost to follow-up in any disposition page	Lost to follow-up

6	No event and [EOS present OR disposition page for any EPOCH after screening says patient will not continue into any subsequent phase of the study] and no adequate post-baseline tumor assessment	No adequate post-baseline tumor assessment
7	No event and none of the conditions in the prior hierarchy are met	Ongoing without an event

For OS, patients last known to be alive are censored at date of last contact.

Date of Last Contact

The date of last contact will be derived for patients not known to have died at the analysis data cutoff date using the latest complete date (non-imputed) among the following:

- All patient assessment dates (e.g., blood draws [laboratory, PK], vital signs, performance status, ECG, tumor assessments, concomitant radiation, surgery)
- Start and end dates of follow-up anti-cancer therapies
- AE start and end dates
- Last date of contact where “Subject Remains in Follow-up” collected on the “Survival Follow-up” eCRF (do not use date of survival follow-up assessment unless status is alive)
- Study drug start and end dates
- Date of discontinuation on disposition eCRF pages (do not use if reason for discontinuation is lost to follow-up or death).

Note:

1. This list is not all inclusive and should be agreed upon by the study team according to the data collected in the CRF

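### A stable scan on a raised steroid dose may not count as adequate, so an on-time week-16 progression in a resected Arm A patient can be censored near the start of follow-up

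*Protocol*

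**What the plan says.** Rating of scans:

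- Protocol 9.3, Stable Disease item 2, requires "Stable non-enhancing (T2/FLAIR) lesions on same or lower dose of corticosteroids compared to baseline scan". It adds that when steroids were raised for new symptoms and later imaging attributes this to progression, "the last scan considered to show stable disease will be the scan obtained when the corticosteroid use was equivalent to the baseline dose". SAP 10.1, Table 2, repeats both sentences.
- A steroid dose above baseline also rules out PR (Protocol 9.3, PR items 4 and 5). CR requires the patient to be off steroids or on physiologic replacement only.
- The footnote to the table in Protocol 9.4 says: "Increase in corticosteroid dose in isolation of other criteria will not be taken into account in the assessment of progressive disease". This exemption applies only when there is no persistent clinical deterioration.

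PFS derivation, SAP 10.2:

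- Note (3): "Adequate radiographical tumor assessment refers to an assessment with overall response of CR, PR, SD or PD".
- Note (1): "Symptomatic deteriorations (i.e. symptomatic progressions, which are not radiographically confirmed) will not be considered as progressions".
- Table 4, hierarchy 3: "Tumor progression (per RANO) documented after 2 scan intervals following previous adequate radiological tumor assessment" is censored, at "Date of previous adequate radiological assessment or Date of first dose, whichever comes later".
- Table 4, last row: "Tumor progression (per RANO) documented within 2 scan intervals following previous adequate radiological tumor assessment" is an event.
- Table 5 words hierarchy 3 as 2 weeks, not 2 scan intervals.

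SAP 8.2.2.2 estimates PFS-6 by Kaplan-Meier with an 80% CI.

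**The concern.** Hierarchy 3 is meant for progressions that follow missed assessments; Table 5 gives that as its reason. Here no visit is missed. The patient attends at week 8, the scan is readable and shows no progression, but the steroid dose is above baseline. If that scan has no rating, the next scan is compared with the baseline MRI or the first dose, and a progression found on schedule can be treated as though the week-8 visit had not happened.

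The row applies only to patients whose progression is documented, and SD item 2 picks out those who were already getting worse. The censoring is therefore tied to the outcome. Removing such patients from the risk set early raises PFS-6, the primary efficacy estimate. Each arm is estimated on its own with no control, so nothing offsets the bias.

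**Working it through.** **1. The plan's own figure.** Protocol 10.2 and SAP 4.2.2: N = 30 per arm, projected PFS-6 20% (6/30), two-sided 80% exact interval. Lower limit = 0.10 quantile of Beta(6, 25) = 10.9%; upper limit = 0.90 quantile of Beta(7, 24) = 32.5%. The statement that the lower bound exceeds 10% reproduces.

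**2. Rating of an otherwise stable scan on a raised dose.** SD, PR and CR are excluded by the steroid conditions. PD is excluded unless clinical deterioration persists. No category is left. The SAP's best-response rules do use a not-evaluable status for single assessments, but no passage assigns it here. The scan being unrated, and so not adequate, is an inference.

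**3. Inputs for the gap.**
- Scan interval 56 days, so 2 intervals = 112 days. The SAP gives no day count or tolerance; 112 is an assumption.
- Scans every 8 weeks from combination Cycle 1 Day 1, each ±7 days (Protocol Appendices A and B).
- Arm A: surgery 7 ± 2 days after first dose; baseline MRI 48-72 hours after surgery; combination starts 15-28 days after surgery (Protocol 4.1, 5.4.2).

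**4. Resected Arm A: week-8 scan not adequate, no interim scan, PD at week 16.**
- MRI to combination start: 15 − 3 = 12 to 28 − 2 = 26 days.
- MRI to week 16: 112 + 12 = 124 to 112 + 26 = 138; with ±7, **117-145 days**.
- First dose to combination start: 5 + 15 = 20 to 9 + 28 = 37 days. First dose to week 16: 132-149; with ±7, **125-156 days**.

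Every value exceeds 112. The PD scan falls on study day 126-157, before month 6 (6 × 30.4375 = 182.6 days). Censoring at the post-operative MRI is on study day 8-13, that is 8/30.4375 = 0.26 to 13/30.4375 = 0.43 months. Had the week-8 scan counted, the gap would be 56 days (42-70 with both windows) and the PD an event.

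**5. Other situations.** Shares are over equally likely window days.

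| Situation | Nominal gap (days) | With windows | Over 112 days |
|---|---|---|---|
| Resected Arm A, PD at week 16, from MRI | 124-138 | 117-145 | 100% |
| Arm B, same pattern, from first dose | 112 | 105-119 | 47% |
| One such scan later, between rated scans, either arm | 112 | 98-126 | 47% |

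Exactly 112 days is within 2 intervals, so rows 2 and 3 are events on the nominal schedule. Counting Arm B from a baseline MRI up to 28 days before first dose would widen its range to 105-147 days. Table 5 refers to a post-baseline scan or the start date, which favours first dose.

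**6. With a tolerance.** For the Arm A pattern, a limit of 119 days (112 + 7) still censors 98% of window combinations, and 126 days (112 + 14) censors 76%. In Arm B from first dose, neither limit censors any.

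**7. Effect on PFS-6 (illustration).** Suppose 24 of 30 progress before month 6 and k of them are censored before the first event. Kaplan-Meier PFS-6 = 6/(30 − k): k = 0, 6/30 = 20.0%; k = 1, 6/29 = 20.7%; k = 3, 6/27 = 22.2%. The 80% log-log lower bound goes from 11.6% (k = 0) to 13.0% (k = 3). The documents give no frequency from which to set k.

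**The case against.** The strongest reply is that no passage says the scan loses its rating in the data. SD item 2 works partly in retrospect, nothing instructs anyone to revise a CRF entry, and SAP 10.1 takes response for ORR from the investigator's CRF assessment. If SD was entered at week 8 and stands, the scan is adequate and the week-16 PD is an event. This stands as a limit on certainty. It does not clear the plan: the first sentence of item 2 bars SD at the time of the scan, so a correct rating and the convenient one conflict.

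There are other ways for the event to survive:

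- Persistent clinical deterioration may lead to a PD rating at week 8. That rating is adequate even though Note (1) stops an unconfirmed symptomatic progression from being an event.
- Protocol 9.3 dates progression back to the first suspicious scan when imaging was equivocal. In Arm A, week 8 is 61-89 days from the post-operative MRI, an event. This does not reach a clearly stable scan.
- An interim PD scan at week 12 is 96-110 days from that MRI, also an event (104-121 from first dose, so mixed).

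Part of the cause is not steroids at all. Arm A scans are timed from combination start, 12-26 days after the baseline MRI, so any missed or unevaluable week-8 scan gives the same gap.

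Finally, the study tests no hypothesis, and in the illustration the lower bound stays above 10% either way. SAP 10.1 permits PFS sensitivity analyses but specifies none.

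**Conclusion.** The defect is real and limited. Applied literally, the rules censor an on-schedule progression, with no visit missed, for resected Arm A patients with an unrated week-8 scan, no interim scan and PD at week 16. That rests on the scan being unrated and on 2 intervals meaning 112 days; with a tolerance, most but not all such cases are still censored. For progressions before month 6 the bias in PFS-6 is upward. Its size is unknown, and 20.0% to 22.2% is only an illustration.

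A reader might infer that every progression after a raised-steroid scan is censored, or that this always happens in Arm A. The documents support neither. In Arm B counted from first dose, and for a single later scan in either arm, the nominal gap is an event and only about half of window combinations are censored. Arm A patients who are not resected are assessed by the Arm B criteria, and their gap is not fixed by the documents. A reader might also infer a definite loss of several events per arm; no frequency of steroid increases is given to support that.

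**What to change.** Add to SAP 10.2 Note (3): *A readable scan without PD counts as an adequate assessment for the 2-scan-interval rule even if it cannot be rated SD because the corticosteroid dose is above baseline.* State that SD item 2 then governs only best overall response and DCR.

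In the same edit:

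- Define 2 scan intervals in days, with one reference date, allowing for the ±7-day windows and for the Arm A delay between post-operative MRI and combination start. The permitted maxima with one unrated scan are 126 days between post-baseline scans and 145 days from the Arm A post-operative MRI.
- Reconcile Table 4 (2 scan intervals) with Table 5 (2 weeks). Read literally, 2 weeks would censor almost every PD found on 8-weekly scans, whatever the steroid dose.

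The cost is a few sentences in the SAP and a change to one derivation. No clinical rule and no data collection changes. The downside is that PFS-6 may come out slightly lower.

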9.4 Evaluation of Best Overall Response

The best overall response is the best response recorded from the start of the treatment until disease progression/recurrence and is determined as indicated in the table below:

The table below provides the summary of the RANO response criteria.

Criterion	Complete Response	Partial Response	Stable Disease	Progressive Disease
T1/Gd enhanced lesions	None	≥50% decrease	≤50% decrease to <25% increase	≥25% increase*
T2/FLAIR	Stable or decreasing	Stable or decreasing	Stable or decreasing	Increasing*
New Lesion	None	None	None	Present*
Corticosteroids	None	Stable or decreasing	Stable or decreasing	NA**
Clinical Status#	Stable or improving	Stable or improving	Stable or improving	Worsening*
Requirement for Response	ALL	ALL	ALL	Any*

*Progressive Disease occurs when any of the criteria marked by * are present.

**Increase in corticosteroid dose in isolation of other criteria will not be taken into account in the assessment of progressive disease in the absence of persistent clinical status deterioration.

#Clinical status will be assessed via ECOG Performance Score

10 PLANNED STATISTICAL METHODS

10.1 General Considerations

Categorical variables will be summarized as the number and percentage of patients in each category. Continuous variables will be summarized by the mean, standard deviation, median, minimum, and maximum.

The primary population for the efficacy endpoints will be the Per Protocol population defined as the population of patients who have been treated with at least 80% of 1 complete cycle of BBI608 and TMZ. Analyses will also be performed on the Intent-to-Treat (ITT) population in each arm. The primary endpoint is PFS-6, defined as the proportion of patients with PFS (i.e. absence of documented objective progression or death) at 6 months after enrollment.

For each of the study arms, the secondary endpoints will include OS, defined as the interval between the date of patient enrollment until death; PFS, defined as the interval between the date of patient enrollment and objective disease progression or death; ORR, the proportion of patients with a documented complete response or partial response according to the RANO criteria; and DCR, the proportion of patients with a documented stable disease, partial response or complete response according to RANO criteria.

10.2 Determination of Sample Size

For each of the study arms, with the a sample size of 30, the lower bound of the two-sided 80% confidence interval, as estimated by the exact binomial method using a projected PFS-6 of 20%, will be greater than 10%, and provides meaningful information for further clinical evaluation.

10.3 Analysis Populations

All patients receiving at least one dose of BBI608 will be considered evaluable for safety analysis. Adverse event incidence rates will be described by the frequency of adverse events, categorized by NCI CTCAE version 4.0. Listings of laboratory test results collected at baseline and during the study will be generated. Descriptive statistics summarizing the changes in those laboratory tests over time will be presented.

For each of the study arms, the primary population for the efficacy endpoints will be the Per Protocol population defined as the population of patients who have been treated with at least 80% of 1 complete cycle of BBI608 and TMZ. Analyses will also be performed on the Intent-to-Treat (ITT) population in each arm. The primary endpoint is PFS-6, defined as the proportion of patients with PFS (i.e. absence of documented objective progression or death) at 6 months after enrollment.

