In the phase Ib/DLT cohort portion of this study, for both Arms A and B, pharmacokinetics will be evaluated on Day 1 and Day 5 of combination therapy with BBI608 and TMZ. Pharmacodynamics will be evaluated in all patients who undergo surgical resection.

For patients in Arm A during the run- in period with BBI608 monotherapy, the same DLT rules as for the combination therapy will apply. Enrollment will be held if ≥ 2 patients are unable to undergo resection due to DLTs. Enrollment will also be held if ≥ 2 patients have an unexpected surgical complication.

Initial enrollment will be to a 6-patient safety cohort in each arm. These patients will be evaluated for the occurrence of DLT during the first 28 days of combination treatment with BBI608 and TMZ. If DLT is observed in ≥ 2 of 6 patients evaluable for DLT, the initial dose of BBI608 for all patients in that arm will be reduced to the next lower dose level of 240mg twice daily and an additional 6-patient safety cohort will be enrolled at that dose-level and evaluated for DLT as above. Enrollment will continue at a dose-level at which ≤ 1 of 6 patients experiences DLT. Dose modification is allowed according to the standard schedule for BBI608.

It is expected that up to 30 patients (including those enrolled to the DLT evaluation cohorts) will be enrolled in each arm.

For all patients on study, tumor assessments will be performed at eight-week intervals or as clinically indicated. Disease status will be assessed by contrast-enhanced magnetic resonance imaging (MRI) of the brain.

Progression Free Survival will be assessed from the date of enrollment until objective disease progression or death. Tumor response and progression will be evaluated using RANO criteria. Patients who are enrolled in Arm A but who do not undergo surgical resection will be considered evaluable for tumor response utilizing the same assessment criteria as employed for patients in Arm B. All patients will be followed for disease progression and included in time-to-event analyses.

Patients will continue treatment with BBI608 and TMZ until the investigator has determined that they are no longer clinically benefiting due to progression of

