6. ANALYSIS SETS

6.1. Full Analysis Set

The full analysis set (FAS) includes all patients who received at least one dose of any study drug

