8.2.2.2. Progression Free Survival at 6 months (PFS-6, Phase 1 and Phase 2)

PFS data will be analyzed by arm. PFS summary in Arm B will be provided only when the number of patients in that arm is at least 10. The same rule applies to Arm A data.

Progression free survival at 6 months (PFS-6) is defined as the proportion of patients who have survived without objective disease progression per RANO criteria for at least 6 months after enrollment. The censoring rules for PFS will be detailed in 10.2. If a patient has not progressed or died at the time of analysis, PFS will be censored on the date of the last tumor assessment. This includes patients who are lost to follow-up or have withdrawn consent.

PFS in months is calculated as (first event date/censored date – date of first dose of any study drug + 1)/30.4375. Estimates of the PFS curves at 6 months will be obtained using the Kaplan-Meier method and will be presented along with the 80% CI using the normal approximation to the log transformed cumulative hazard rate.

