8.2.3. Analyses for Secondary Endpoints

8.2.3.1. Other Efficacy Endpoints Analysis

Response data (including Disease Control Rate (DCR) and Objective Response Rate (ORR)), progression free survival (PFS) and overall survival (OS) data will be analyzed by arm. Response data summary for Arm B will be provided only when the number of patients in that arm is at least 5. The same rule applies to Arm A data. Otherwise, only response data listing will be provided.

Summary for survival data (including PFS and OS) will follow the rule of ‘at least 10’ as described in Section 8.2.2.2.

DCR is defined as the proportion of patients with a documented complete response, partial response, and stable disease (CR + PR + SD) based on RANO. The primary estimate of DCR will be based on the FAS population. DCR will be summarized for each treatment arm along with the corresponding exact 2-sided 95% CI using the Clopper Pearson method.

ORR is defined as the proportion of patients with a documented complete response and partial response (CR + PR) based on RANO. The primary estimate for ORR will be based on the FAS population.

ORR will be analyzed similarly as DCR. Best Overall Response (BOR) will also be summarized in a similar fashion.

PFS in the full analysis set is defined as the time from exposure to any study drug to the first objective documentation of disease progression or death due to any cause. If a patient has not progressed or died at the time of analysis, PFS will be censored on the date of the last tumor assessment. PFS is calculated as described in section 8.2.2.2.

PFS will be reported as the median event time (and other quartiles) and the corresponding 2-sided 95% CI for each treatment arm. Estimates of the PFS curves obtained from the Kaplan-Meier method will be presented along with a graphical presentation of PFS curves.

OS is defined as the time from exposure to any study drug to death from any cause. Patients who are alive at the time of analysis or who have dropped out will be censored at their last date known to be alive. OS in months is calculated as $(\text{date of death/Last known to be alive date} - \text{date of first dose of any study drug} + 1)/30.4375$.

The survival experience of patients will be summarized by the Kaplan-Meier method.

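### The protocol's primary population for PFS-6 is a Per Protocol set chosen on treatment received after the first dose; the SAP implies the full analysis set instead and records no departure

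*Protocol*

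**What the plan says.** The Protocol Synopsis (Statistical Methods), 10.1 and 10.3 name this set as primary for the efficacy endpoints: "Per Protocol population defined as the population of patients who have been treated with at least 80% of 1 complete cycle of BBI608" (TMZ is held to the same rule). ITT analyses are planned in addition. PFS-6 is the proportion alive without objective progression 6 months after enrollment. Protocol 7.3 has diary compliance monitored so that the Per Protocol set can be verified, so the rule was meant to be used.

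The SAP is based on the same protocol, dated March 9, 2017. Its section 6 defines three sets: full analysis, PK and PD/Biomarker. "The full analysis set (FAS) includes all patients who received at least one dose of any study drug". No Per Protocol or ITT set appears. For the primary endpoint, SAP 8.2.2.2 says "Estimates of the PFS curves at 6 months will be obtained using the Kaplan-Meier method", by arm with an 80% CI, and names no set. SAP 8.2.3.1 puts DCR and ORR on the FAS. It then says "PFS in the full analysis set is defined as the time from exposure to any study drug to the first objective documentation" of progression or death, and adds "PFS is calculated as described in section 8.2.2.2".

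SAP 10.2, Table 4, decides how early losses count. A patient with "No post baseline radiological tumor assessment available and no death reported within 2 scan intervals" of first dose is censored at first dose. Symptomatic deteriorations "which are not radiographically confirmed) will not be considered as progressions".

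**The concern.** A patient enters the Per Protocol set only after receiving enough treatment, but the PFS clock starts earlier. Anyone who dies in between cannot be a member, and each such death is a PFS-6 failure taken out of the denominator. This is guarantee-time selection. It is potentially strongest in Arm A, where run-in, surgery and recovery come before combination therapy and where Protocol 4.1 withdraws patients who have not recovered within 28 days of surgery.

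PFS-6 is the Phase II primary endpoint, and SAP 4.1 plans no hypothesis test, so the estimate and its interval are the result. The two documents lead to different primary figures. A report that follows the SAP would present a PFS-6 that is not the one the protocol calls primary, with no recorded explanation.

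**Working it through.** **1. The plan's own figure.** Protocol 10.2: n = 30 per arm, projected PFS-6 20%, exact two-sided 80% interval. For 6/30 this is 10.9% to 32.5%, so the stated lower bound above 10% reproduces. It refers to 30 patients. The denominator can matter at that mark: by the same exact method 5/30 has a lower bound of 8.3%, while the same 5 successes among 25 (5 failures excluded) give 10.06%.

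**2. When membership is settled.** The cycle is 28 days (Protocol 4.1), and 0.8 × 28 = 22.4 days of BBI608 with no missed doses. TMZ is given on days 1 to 5, so BBI608 sets the limit.
- Arm B: about 22 days after first dose.
- Arm A: run-in 5 to 9 days, then 15 to 28 days after surgery, then 22.4 days. This gives 5 + 15 + 22.4 = 42.4 to 9 + 28 + 22.4 = 59.4 days.

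**3. How such patients count in the FAS.** Two scan intervals are 2 × 8 weeks = 112 days. A death before day 59 with no post-baseline scan is therefore an event under Table 4, unless a higher-ranked censoring rule applies. A patient alive, with no post-baseline scan and no death in that time, is censored at first dose and adds nothing to the estimate.

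**4. Illustration.** Assumptions: 30 treated, 6 event-free at 6 months and all of them in the Per Protocol set, 6 patients outside it, no other censoring before 6 months. With n the number not censored at first dose, S = 6/n. The 80% interval is S^exp(±z·v), where v = √(S(1−S)/n) / (S·|ln S|) and z = 1.2816. This is the log-transformed cumulative hazard interval of SAP 8.2.2.2.

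| Analysis | n | PFS-6 | 80% CI | Per Protocol minus FAS |
|---|---|---|---|---|
| Per Protocol | 24 | 25.0% | 14.6–36.8% | – |
| FAS, all 6 have early events | 30 | 20.0% | 11.6–30.0% | 5.0 points |
| FAS, 3 events, 3 censored at first dose | 27 | 22.2% | 13.0–33.1% | 2.8 points |
| FAS, all 6 censored at first dose | 24 | 25.0% | 14.6–36.8% | 0 |

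With 3 patients outside instead of 6, Per Protocol is 6/27 = 22.2% and the FAS runs from 20.0% to 22.2%, a gap of 2.2 to 0 points.

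**5. Direction.** Keep 6 event-free among the 30 and 6 outside, but let some of those outside be event-free.
- 1 of the 6: Per Protocol 5/24 = 20.8%. FAS 6/30 = 20.0% if the other 5 have events, or 6/25 = 24.0% if they are censored at first dose.
- 2 of the 6: Per Protocol 4/24 = 16.7%. FAS 6/30 = 20.0%, or 6/26 = 23.1%.

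The bias is therefore upward when excluded patients die early, and can turn downward when they are event-free.

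**The case against.** The strongest reply is that the SAP governs the analysis and already points to the less selective set, so the biased figure is not the one that will be produced. That stands as far as it goes: the proposed change does not alter the number the SAP implies. It does not remove the disagreement over which figure is primary, and the primary endpoint is left with the least explicit population of all the efficacy endpoints.

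It is also fair to say that the gap may be small. The illustrative range of 0 to 5 points compares with an 80% interval 30.0 − 11.6 = 18.4 points wide. Eligibility (ECOG 0–1, life expectancy of at least 3 months) limits early deaths, mainly in Arm B. The first scheduled response scan comes about 8 weeks after combination therapy starts, later than the 22 days of combination treatment that membership needs, and treatment may continue after radiological progression. Events recorded before the threshold would be mainly deaths or findings on unscheduled scans. Rescaling PFS-6 as if every early event barred membership would overstate the bias.

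Four stronger readings are tempting, and the documents do not support them.
- That the protocol contradicts itself because its Synopsis says "All patients will be followed for disease progression and included in time-to-event analyses". The planned ITT analyses satisfy that sentence.
- That the Per Protocol figure cannot be produced. Protocol 10.3 gives the 80% rule, and 7.3 gives a compliance formula and a diary.
- That moving to the FAS cures all the selection. An Arm A patient withdrawn alive after surgery with no post-baseline scan is censored at first dose, so the FAS recovers no information on that patient.
- That silence in the SAP's amendment section proves an unrecorded change. That section compares SAP versions. The point rests on the whole available SAP text, and its front matter was not available.

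**Conclusion.** The point holds and should be fixed. The protocol makes primary a set that can drop early deaths from the PFS-6 denominator. The SAP uses the FAS for DCR, ORR and PFS, implies it for PFS-6 through 8.2.3.1, and neither names it in 8.2.2.2 nor records the departure. The size is unknown because no exclusion rate is given. With 3 to 6 of 30 patients outside the Per Protocol set and none of them event-free, it would exceed the FAS figure by 0 to 5.0 points. If some of those excluded are event-free, it can fall below the FAS figure, for example 16.7% against 20.0% or 23.1%. These figures assume no other censoring before 6 months. The choice of the FAS is sound; the fault is that it is not stated for the primary endpoint and conflicts with the protocol without explanation.

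**What to change.** - In SAP 8.2.2.2, state that the primary analysis of PFS-6 is the Kaplan-Meier estimate in the full analysis set, by arm, and that every treated patient, including those replaced under Protocol 11.3, is in the set and handled by Table 4.
- Report by arm how many FAS patients are censored at first dose.
- In SAP section 6, define the Per Protocol set by the protocol's 80% rule, for a sensitivity analysis only. SAP 8.2.1 plans TMZ compliance overall only, so cycle 1 TMZ compliance would have to be derived.
- Align the Protocol Synopsis, 10.1 and 10.3. Since SAP 8.1.1 says follow-up has ended, the practical alternative is to record the departure and its reason in the SAP. State there that ITT is taken as the FAS, with enrollment at first dose as in Protocol 11.2 (5.1 instead places enrollment at eligibility and consent).

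The cost is a few sentences in the SAP, plus a short protocol alignment or a recorded departure. No new data collection is planned. The primary PFS-6 may be slightly lower than the protocol's Per Protocol figure.
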